## **5. ANALYSIS SAMPLES**

The Efficacy Population will include all patients who are randomized in the study, dispensed study drug, and have at least 1 post-treatment SALT assessment.

The Safety Population will include all patients who receive study drug during the Treatment Period.

The Pharmacokinetic (PK) population will include all patients who received study drug in Part A, Period 1 and had at least 1 post-treatment blood draw.

All populations will be analyzed by the treatment received. In the event patients incorrectly receive treatment associated with a different treatment group per Part and/or Period of the study, they will be analyzed “as treated” if the patient received that treatment for more than 50% of doses for that Period/Part.

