Event	Day -28 to Day -1 (Visit 1)	Randomization ^{1, 2} Day 1 (Visit 2)	Week 2 (Visit 3)	Week 4, 8 (Visit 4, 5)	Week 12 (Visit 6)	Week 16, 20 (Visit 7, 8)	Week 243,4 (Visit 9)	Week 28 ⁵ (Visit 10)	Week 32 (Visit 11)	Week 36 (Visit 12)	Week 40, 44 (Visit 13, 14)	Week 484 (Visit 15)	Safety Follow-Up Visit
Informed consent	X												
Eligibility assessment	X	X											
Demographics	X												
Medical history	X	X											
Randomization		X					X^7						
PE	X	X					X					Х	X
Brief PE				X	X	X			X	X	Х		
Height	X												
Weight	X	X		X	X	X	X		X	X	X	X	X
Pregnancy test ⁸	X	X ⁹		X	X	X	X	X	X	X	X	X	
Tuberculosis test	X												
Clinical laboratory testing ¹⁰ , 11	X ¹²	X	X	X	X	X	X	X	X	X	X	X	X
Lipid assessment ¹³		X			X		X			X		X	X
HBV and HCV test	Х												
12-lead electrocardiogram	Х	X			Х		X			X		Х	X
Vital signs	X	X		X	X	X	X		X	X	Х	X	X
SALT assessment	Х	X		X	X	X	X	X^{14}	X^{14}	X^{14}	X14	Х	
Photographs	X	X		X	X	X	X	X	X	X	Х	X	
SPRO and QPRO		X			X	X	X						
CGI-S and PGI-S		X			Х	X	X						
CGI-I and PGI-I					X	X	X						
Dispense study drug		X		X	X	X	X^7	X^{15}	X^{15}	X^{15}	X15		
Pharmacokinetic blood sampling ¹⁶		X			X		X						
Study drug accountability				X	X	X	X		X	X	X	X	_
Adverse events	X				X					X			X
Concomitant medications	X		X			X				X			

PE = Physical Examination; HBV= hepatitis B virus; HCV = hepatitis C virus; SPRO = Satisfaction of Hair Patient Reported Outcome; QPRO = Quality of Hair Patient Reported Outcome; CGI-S = Clinical Global Impression of Severity; CGI-I = Clinical Global Impression of Improvement; PGI-S= Patient Global Impression of Improvement; PGI-I = Patient Global Impression of Improvement;

- ¹ Day 1 (Visit 2) may occur any time after Screening laboratory results are available and reviewed by the Investigator.
- ² For Part A, Period 1, all subsequent visits and week increments should be based on the date of Visit 2. All visit windows are ± 2 days.
- ³ Week 24 from Part A, Period 1 will also serve as the Day 1 visit for Part A, Period 2 for those who meet criteria to continue into the Dose Modification Phase.
- ⁴ Also serves as the Early Termination Visit for patient withdrawal in this period.
- ⁵ For Part A, Period 2, all subsequent visits and week increments should be based on the date of Week 24 (Visit 9). All visit windows are ±2 days.

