13.3. Analysis Populations

The Efficacy Population will include all patients who receive study drug and have at least 1 post-treatment SALT assessment. The Safety Population will include all patients who receive study drug. Patients will be summarized according to study drug dose received (i.e., as treated) should it differ from the randomized arm. The PK population will include all patients who received study drug in Part A, Period 1 and had at least 1 post-dose blood draw.

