#### 4. GENERAL ANALYSIS AND REPORTING CONVENTIONS

The following is a list of general analysis and reporting conventions to be applied to this study, unless otherwise specified. Departures from these general policies will be described, if applicable, in the appropriate sections of this SAP. When this situation occurs, the rules set forth in the specific section take precedence over the general policies.

All data displays (tables, listings, and figures) will have a header showing the sponsor company name, protocol number, page number, and display status (i.e. “DRAFT” or “FINAL”), as well as a footer indicating file name and run date/time. Summary tables and data listings will be summarized by treatment group for efficacy and exposure, and by treatment group and overall otherwise. All data for analysis may be listed by-patient.

Specifically, for each Part and Period of the study, the summary table layout will be as follows:

For Part A, Period 1 tables:

Treatment Phase		
CTP-543 8 mg BID	CTP-543 12 mg BID	Total

For Part A, Period 2 tables:

Dose Reduction		Drug Discontinuation		Total
CTP-543 8 mg BID to 4 mg BID	CTP-543 12 mg BID to 8 mg BID	CTP-543 8 mg BID to Placebo	CTP-543 12 mg BID to Placebo	

For Part B tables:

Dose Reduction		Drug Discontinuation		Total
CTP-543 8 mg BID to 4mg BID to 8 mg BID	CTP-543 12 mg BID to 8 mg BID to 12 mg BID	CTP-543 8mg BID to Placebo to 8 mg BID	CTP-543 12 mg BID to Placebo to 12 mg BID	

Note that for all efficacy and exposure tables, the total column will not be displayed.

Categorical variables will be summarized using counts (n) and percentages (%) and will be presented in the form “n (xx.x).” If a count is 0, no percentage will be shown. If a percentage is 100%, 100 will be shown. To ensure completeness, summaries for categorical variables will include all categories, even if no patients had a response in a particular category. Unless otherwise specified, the denominator for each percentage will be based on the number of patients in the population being summarized (header n). Percentages will be rounded to one decimal place.

Continuous variables will be summarized using mean, standard deviation, minimum, maximum, median, and number of patients. The minimum and maximum will be the same precision as the

Concert Pharmaceuticals, Inc.  
Statistical Analysis Plan – CP543.2004

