## **8.2. Primary Endpoints**

### Part A:

This study is designed to be exploratory and descriptive in nature and no formal hypothesis testing is planned. Therefore, descriptive statistics will be used to summarize the results regarding dose modification following successful hair regrowth for each dose group. In Part A, Period 1, a Responder is defined as having an absolute SALT score  $\leq 20$  at Week 24 of the Treatment Period. Only Responders will enter into Part A, Period 2 (Dose Modification) for the primary efficacy analysis. For Part A of the study, there are two co-primary efficacy endpoints. The first co-primary efficacy endpoint is the percentage of patients achieving LOM criteria (SALT  $> 20$ ) compared to the percentage of patients maintaining treatment success (SALT  $\leq 20$ ) for each of the following dose reduction conditions (Period 2 ONLY):

- 12 mg BID reduced to 8 mg BID
- 8 mg BID reduced to 4 mg BID

The second co-primary efficacy analysis is the percentage of patients achieving LOM criteria compared to the percentage of patients maintaining treatment success for each of the following drug discontinuation conditions (Period 2 ONLY):

- 12 mg BID to Placebo
- 8 mg BID to Placebo

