### **8.2.1. Computation of the Primary Endpoints**

The SALT is a measure of hair loss that quantifies the amount of scalp surface without hair in a pre-specified quadrant of the scalp (right side, top, left side, back), that is further summed after applying a quadrant-specific multiplier indicative of scalp surface area contribution, to provide an overall score of total hair loss. An example of the SALT assessment can be found in Appendix 18.2 of protocol.

The primary endpoints for each Part of the study consist of deriving and categorizing the individual overall SALT scores ( $\leq 20$  versus  $> 20$ ).

Due to the variable time on study for each patient within Part A Period 2, the primary analysis visit will be the End of Part A Period 2, where the last observed non-missing SALT value is selected for each patient. Otherwise, missing data will not be imputed for this descriptive, exploratory study.

Patterns of missing values across visits will be listed and summarized with numbers and percentages by treatment and visit.

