### **8.2.2. Primary Analysis of the Primary Endpoints**

This study is designed to be exploratory and descriptive in nature and no formal hypothesis testing is planned. Therefore, descriptive statistics will be used to summarize the results for each Part/Period.

The observed number and percentage of patients with an absolute SALT score  $\leq 20$  versus those with an absolute SALT score  $> 20$ , will be reported by treatment group with 95% confidence intervals (using the binomial approximation with a Wald continuity correction). This analysis will be completed for the Efficacy Population. The results may also be displayed graphically. No p-values will be reported.

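### A re-randomised patient with no Period 2 SALT stays in the co-primary analysis, and either reading of the SAP normally lowers the loss-of-maintenance percentage.

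*SAP*

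**What the plan says.** SAP Section 5 defines the population once: "The Efficacy Population will include all patients who are randomized in the study, dispensed study drug, and have at least 1 post-treatment SALT assessment". Protocol Section 13.3 does the same: "The Efficacy Population will include all patients who receive study drug and have at least 1 post-treatment SALT assessment". Neither ties the SALT requirement to a Part or Period. SAP Section 8.2.2 applies this population to the co-primary endpoints: "This analysis will be completed for the Efficacy Population".

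The value analysed is set in SAP Section 8.2.1. Because time in Period 2 varies, the analysis visit is the End of Part A Period 2, "where the last observed non-missing SALT value is selected for each patient". The section then adds: "Otherwise, missing data will not be imputed for this descriptive, exploratory study". SAP Section 4 sets the default denominator: "the denominator for each percentage will be based on the number of patients in the population being summarized (header n").

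Three further provisions bear on which SALT can be the latest one:

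- Protocol Table 1, footnote 3: "Week 24 from Part A, Period 1 will also serve as the Day 1 visit for Part A, Period 2".
- SAP Section 6.2 makes that Week 24 SALT the Period 2 baseline. SAP Section 4 starts Period 2 treatment on the re-randomisation date and assigns a shared treatment day to Period 2.
- SAP Section 8.2: "Only Responders will enter into Part A, Period 2 (Dose Modification) for the primary efficacy analysis". SAP Section 4 notes that scores were rounded to the nearest integer when patients were moved between periods, whereas analyses use unrounded scores.

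SAP Section 8.2.3 specifies no sensitivity analysis.

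**The concern.** In Period 2 the SALT requirement screens out nobody, since each entrant has Period 1 scores, including the one that admitted them. For a patient never assessed after re-randomisation, the co-primary outcome could then be the entry criterion itself. If the entry score is not used, the patient has no outcome but remains in the denominator. In neither case has the patient given any information about maintenance on the new regimen, yet the reported LOM percentage is affected. Table 14.2.1.1, which carries this result, is marked for the abbreviated report that supports the NDA.

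**Working it through.** **Plan's own figure.** Protocol Section 13.1 expects about 50 responders per dose group, and Section 8.3 re-randomises them 1:1. 50 × 1/2 = 25 per arm, which agrees with the stated 25. The Period 1 totals also agree: 170 + 130 = 300. The study is descriptive, so there is no power calculation to reproduce.

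**What happens to a patient with no Period 2 SALT**

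1. Membership is met on Period 1 scores, so the patient is in the header n.
2. Reading A: the Week 24 SALT is eligible because it is also the Period 2 Day 1 value. A program that keeps assessments dated from the start of Period 2 would pick it up. Entry required a rounded score of 20 or less, so the patient is normally classed as maintained.
3. Reading B: the endpoint's restriction to Period 2 rules the entry score out. No value exists and none is imputed. The patient counts as neither outcome but stays in the header n.

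**Effect on LOM.** Let n = 25 re-randomised, x = observed LOM, and k = patients with no Period 2 SALT. Only n comes from the documents; x and k are assumptions.

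- As written, reading A (entry score 20 or less) or B: x/n
- Excluded: x/(n − k)
- Counted as LOM: (x + k)/n

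| x | k | As written | Excluded | Counted as LOM |
|---|---|---|---|---|
| 10 | 1 | 10/25 = 40.0% | 10/24 = 41.7% | 11/25 = 44.0% |
| 10 | 2 | 10/25 = 40.0% | 10/23 = 43.5% | 12/25 = 48.0% |
| 10 | 3 | 10/25 = 40.0% | 10/22 = 45.5% | 13/25 = 52.0% |
| 15 | 1 | 15/25 = 60.0% | 15/24 = 62.5% | 16/25 = 64.0% |
| 15 | 2 | 15/25 = 60.0% | 15/23 = 65.2% | 17/25 = 68.0% |
| 15 | 3 | 15/25 = 60.0% | 15/22 = 68.2% | 18/25 = 72.0% |

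Against exclusion, LOM is lower by 1.7 to 5.5 points at x = 10 and by 2.5 to 8.2 points at x = 15. Against counting as LOM, it is lower by 1/25 = 4 points per patient.

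**Effect on maintenance (x = 10, k = 1).** Reading A gives 15/25 = 60.0%, reading B gives 14/25 = 56.0%, and exclusion gives 14/24 = 58.3%. The two readings agree on LOM but move maintenance in opposite directions from exclusion.

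**Scale against the planned interval.** The SAP's Wald interval with continuity correction is p ± [1.96√(p(1 − p)/n) + 1/(2n)]. At 10/25 this is 0.40 ± (0.192 + 0.020), or 18.8% to 61.2%. The shift from one or two patients is small beside that width.

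**The case against.** The best defence is that the plan means Period 2 values only. The endpoint is limited to Period 2, the analysis visit is named for the end of that period, a baseline is not ordinarily an outcome, and SAP Section 6.1 counts the Efficacy Population separately among Period 2 patients. This is fair evidence of intent. It does not close the gap, because the Period 2 reading leads to reading B, where the patient still dilutes the LOM percentage.

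The second defence is that such patients should be rare, and this largely stands. Protocol Section 9.3 keeps patients who stop drug, but do not withdraw consent, on all visits with efficacy collected. The Week 48 visit, which includes SALT, doubles as the early termination visit. Section 10.2.1 asks for an early termination visit when consent is withdrawn. Period 2 drug is dispensed only while SALT remains at 20 or less. A patient must miss every Period 2 SALT and the termination SALT. That remains possible: Section 11.2 omits SALT when COVID-19 prevents attendance, and consent can be withdrawn at any time.

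Third, the missing-SALT summary (Table 14.2.2.7.2) and Listing 16.2.6.1.3 would expose these patients. They would, but the co-primary percentage would not change.

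A reader might also infer three stronger points that the documents do not support:

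- **That LOM is understated mainly on placebo.** No dropout rate by arm is given, and return to the original dose on LOM is a reason to attend SALT visits.
- **That carrying the entry score forward always favours maintenance.** An unrounded entry score above 20 but below 20.5 would be classed as LOM.
- **That Part B has the same carry-forward fault.** Its primary endpoint is fixed at Week 24 of re-treatment, the latest-value rule is written for Part A Period 2 only, and entrants are above 20, so none can meet restoration on the entry score.

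**Conclusion.** The gap is real but modest. As written, a re-randomised patient with no Period 2 SALT remains in the co-primary analysis, and both available readings lower LOM relative to exclusion, apart from the narrow rounding case under reading A. With 25 per arm and 10 LOM events, the effect is 1.7 points per single patient against exclusion and 4 points against coding as LOM. The number of such patients is not in the documents and is probably small; the event counts used here are illustrative. The text permits classification on the entry score but does not mandate it. A reader might conclude that these patients must be counted as failures in the primary analysis. That does not follow: it is a debatable choice which departs from the SAP's stated policy of not imputing. What is needed is an explicit rule fixed before the database freeze.

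**What to change.** 1. In SAP Section 5, for Part A Period 2 summaries, define the Efficacy Population as re-randomised patients who were dispensed Period 2 drug and have one or more SALT scores after Period 2 Day 1.
2. In SAP Section 8.2.1, restrict the End of Part A Period 2 value to SALT taken after Period 2 Day 1.
3. Report by arm the number of re-randomised patients with no such SALT.
4. Optionally, add a supportive tabulation that keeps these patients in the denominator and counts them as not maintained, to show the range.

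The cost is a few SAP sentences and one extra row in a table, with no change to data collection. The downside is small: the denominator may shrink slightly, and maintenance may look slightly less favourable than if entry scores were carried forward.

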## 6. STUDY SUBJECTS

### 6.1. Disposition of Subjects

Disposition will be summarized by randomized treatment group and overall for all patients screened in the study for each of Part A Period 1, Part A Period 2, and Part B. The number and percentage of patients who are randomized, treated, prematurely discontinued, and completers will be summarized. Unless otherwise specified, percentages will be based on the number of patients randomized in the applicable study part.

The following disposition information will be summarized for Part A Period 1:

- The number of patients screened. Patients who rescreened will be counted only once.
- The number of patients randomized.
- The number and percentage of randomized patients within the Efficacy, Safety, and PK Populations.
- The number and percentage of randomized patients who:
  - completed treatment in Part A Period 1 per the *Treatment Discontinuation/Completion* eCRF page, where completed includes the following subcategories: complete-entering Part A Period 2, complete-entering Open Label, and complete-safety follow-up.
  - prematurely discontinued treatment in Part A Period 1.
    - The frequency and percentage of each discontinuation reason. The denominator for the percentage of each discontinuation reason will be the number of patients who discontinued treatment in Part A Period 1.
  - prematurely discontinued treatment in Part A Period 1 due to COVID-19
    - The frequency and percentage of reasons related to COVID-19. The denominator for the percentage of reasons related to COVID-19 will be the number of patients who discontinued treatment due to COVID-19.
  - completed the study in Part A Period 1 per the *Study Discontinuation/Completion* eCRF page, where completed includes the following subcategories: complete-entering Part A Period 2, complete-entering Open Label, and complete-safety follow-up.
  - prematurely discontinued the study in Part A Period 1.
    - The frequency and percentage of each study discontinuation reason. The denominator for the percentage of each discontinuation reason will be the number of patients who discontinued the study in Part A Period 1.
  - prematurely discontinued the study due to COVID-19
    - the frequency and percentage of reasons related to COVID-19. The denominator for the percentage of reasons related to COVID-19 will be the number of patients who discontinued treatment due to COVID-19.

Concert Pharmaceuticals, Inc.  
Statistical Analysis Plan – CP543.2004

The following disposition information will be summarized for Part A Period 2:

- The number of patients randomized.
- The number and percentage of randomized patients within the Efficacy and Safety Populations.
- The number and percentage of randomized patients who:
  - completed treatment in Part A Period 2 per the *Treatment Discontinuation/Completion* eCRF page, where completed includes the following subcategories: complete-LOM achieved-entering Part B, complete-entering Open Label, and complete-safety follow-up.
  - prematurely discontinued treatment in Part A Period 2.
    - The frequency and percentage of each discontinuation reason. The denominator for the percentage of each discontinuation reason will be the number of patients who discontinued treatment in Part A Period 2.
  - prematurely discontinued treatment in Part A Period 2 due to COVID-19
    - The frequency and percentage of reasons related to COVID-19. The denominator for the percentage of reasons related to COVID-19 will be the number of patients who discontinued treatment due to COVID-19.
  - completed the study in Part A Period 2 per the *Study Discontinuation/Completion* eCRF page, where completed includes the following subcategories: complete-LOM achieved-entering Part B, complete-entering Open Label, and complete-safety follow-up.
  - prematurely discontinued the study in Part A Period 2.
    - The frequency and percentage of each study discontinuation reason. The denominator for the percentage of each discontinuation reason will be the number of patients who discontinued the study in Part A Period 2.
  - prematurely discontinued the study due to COVID-19
    - the frequency and percentage of reasons related to COVID-19. The denominator for the percentage of reasons related to COVID-19 will be the number of patients who discontinued treatment due to COVID-19.

The following disposition information will be summarized for Part B:

- The number of patients re-randomized.
- The number and percentage of re-randomized patients within the Efficacy and Safety Populations.

Concert Pharmaceuticals, Inc.  
Statistical Analysis Plan – CP543.2004

- The number and percentage of re-randomized patients who:
  - completed treatment in Part B per the *Treatment Discontinuation/Completion* eCRF page, where completed includes the following subcategories: complete-entering Open Label and complete-safety follow-up.
  - prematurely discontinued treatment in Part B.
    - The frequency and percentage of each discontinuation reason. The denominator for the percentage of each discontinuation reason will be the number of patients who discontinued treatment in Part B.
  - prematurely discontinued treatment in Part B due to COVID-19
    - The frequency and percentage of reasons related to COVID-19. The denominator for the percentage of reasons related to COVID-19 will be the number of patients who discontinued treatment due to COVID-19.
  - completed the study in Part B per the *Study Discontinuation/Completion* eCRF page, where completed includes the following subcategories: complete-entering Open Label and complete-safety follow-up.
  - prematurely discontinued the study in Part B.
    - The frequency and percentage of each study discontinuation reason. The denominator for the percentage of each discontinuation reason will be the number of patients who discontinued the study in Part B.
  - prematurely discontinued the study due to COVID-19
    - the frequency and percentage of reasons related to COVID-19. The denominator for the percentage of reasons related to COVID-19 will be the number of patients who discontinued treatment due to COVID-19.

The number and percentage of patients randomized within each treatment group will also be summarized by investigative site for each Part and Period of the study.

Disposition and patient visits will also be presented for each patient in patient data listings. Patient data listings will list date of informed consent, date of first/last treatment, date of end of treatment/early treatment termination, date of end of study/early study termination, and reasons for treatment or study discontinuation. A Kaplan Meier curve of time to early treatment termination for any reason by study part will also be presented for the Safety Population. Patients who have completed treatment will be censored at date of last treatment or a maximum of 24 weeks. Consort diagrams may also be presented.

Screen failures will be provided in a separate listing. Rescreened patients who later enrolled will not be listed as screen failures.

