9.3. Patient Withdrawal Criteria

For all patients, it is the intent that patients who discontinue study medication (at any time) for any reason but do not withdraw consent will continue to be followed for all protocol-planned study visits through the completion of the 24-week treatment period, and will have all endpoints (including efficacy) collected accordingly.

The Investigator, Sponsor, or its designee may decide a patient should discontinue treatment at any time and for any reason. In addition, patients will discontinue randomized treatment if they:

- Experience an intolerable adverse event: such events include, but are not limited to, adverse event ≥ Grade 4*, bone marrow-related events, a ≥ Grade 3* cardiac event (*CTCAE v5.0 criteria);
- Require a medication that is prohibited by the protocol. However, under certain circumstances, and in consultation with the Medical Monitor, short-term use of a prohibited medication may not necessitate withdrawal of treatment when its use is unlikely to unfavorably alter the risk-benefit of subject participation;
- In the opinion of the Investigator, have any medically appropriate reason;
- Become pregnant;
- Have a serious adverse event associated with a SARS-CoV-2 infection;
- The Investigator believes that further treatment is undesirable or the risk-benefit profile has become unfavorable.

Furthermore, dose interruptions lasting more than 21 days may require treatment discontinuation on a case by case basis following consultation with the Medical Monitor.

In addition, patients are free to withdraw from participation in the study at any time, for any reason, and without prejudice. The Investigator must withdraw any patient from the study if the patient withdraws consent and requests to stop participating in the study.

Patients who withdraw or are withdrawn from the study will not be replaced.

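### SAP 6.1 divides COVID-19 reasons for leaving the study by the number who stopped treatment for COVID-19, so these sub-line percentages are wrong whenever the two counts differ

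*SAP*

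**What the plan says.** SAP Section 6.1 gives a disposition list for each of Part A Period 1, Part A Period 2 and Part B. Each list has four discontinuation rows: treatment for any reason, treatment due to COVID-19, study for any reason, and study due to COVID-19. Each row has a sub-line for reasons with its own denominator.

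Under the fourth row, "prematurely discontinued the study due to COVID-19", the sub-line says: "The denominator for the percentage of reasons related to COVID-19 will be the number of patients who discontinued treatment due to COVID-19". The same denominator appears under the second row, where it fits: "The frequency and percentage of reasons related to COVID-19. The denominator for the percentage of reasons related to COVID-19 will be the number of patients", again ending with those who stopped treatment for COVID-19. The wording is the same in all three lists.

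The row for leaving the study for any reason, immediately above, uses a matching denominator. For Part A Period 1: "The denominator for the percentage of each discontinuation reason will be the number of patients who discontinued the study in Part A Period 1".

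The section also sets a default: "Unless otherwise specified, percentages will be based on the number of patients randomized in the applicable study part". Study status is taken from its own form ("completed the study in Part A Period 1 per the *Study Discontinuation/Completion* eCRF page"), separate from the form that records treatment completion or discontinuation.

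On follow-up after stopping drug, Protocol 9.3 states the intent that "patients who discontinue study medication (at any time) for any reason but do not withdraw consent will continue to be followed".

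**The concern.** A percentage of reasons should describe the patients who had the event. Here the numerator counts patients who left the study because of COVID-19, and the denominator counts patients who stopped treatment because of it. Neither group contains the other. Under Protocol 9.3, a patient can stop drug for COVID-19 and stay under observation. A patient can also leave the study for COVID-19 after completing treatment, or after stopping drug for some other reason.

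The pattern within each list suggests a copied phrase and not a choice. Three of the four rows pair like with like, and only the COVID-19 study row does not. The SAP gives no reason for the exception, and its Section 13 on changes from the protocol does not mention one.

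The affected outputs are Tables 14.1.1.1, 14.1.1.2 and 14.1.1.3. SAP Appendix 15.4 marks the first two for the abbreviated report that supports the NDA. A programmer who follows the text prints a mismatched percentage. One who corrects it silently departs from the plan, and SAP Section 2 requires deviations to be described in the report.

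**Working it through.** The documents give no figure to reproduce, because the point concerns the definition of a denominator. The check compares the rows and then works through possible counts.

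**Rows as written (same in all three lists)**

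| Row | Numerator: reasons among patients who | Denominator: patients who | Match |
|---|---|---|---|
| Treatment, any reason | stopped treatment | stopped treatment | yes |
| Treatment, COVID-19 | stopped treatment for COVID-19 | stopped treatment for COVID-19 | yes |
| Study, any reason | left the study | left the study | yes |
| Study, COVID-19 | left the study for COVID-19 | stopped treatment for COVID-19 | **no** |

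The default of randomized patients does not apply to the last row, because a denominator is specified there.

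**Inputs.** For one Part/Period, let S be the number who left the study for COVID-19 and T the number who stopped treatment for COVID-19. The documents give neither, so the values below are assumptions chosen to show the range. One recorded reason per patient is also assumed.

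**Formulas.** If reason k has count r_k and the r_k sum to S, then:

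- as written, the percentage for reason k is 100 × r_k / T, and the reasons total 100 × S / T;
- with a matched denominator, it is 100 × r_k / S, and the reasons total 100 × S / S = 100%.

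| T | S | Total as written | Total if matched |
|---|---|---|---|
| 3 | 3 | 3/3 = 100% | 100% |
| 4 | 2 | 2/4 = 50% | 100% |
| 4 | 1 | 1/4 = 25% | 100% |
| 2 | 3 | 3/2 = 150% | 100% |
| 1 | 3 | 3/1 = 300% | 100% |
| 0 | 1 | 1/0, undefined | 100% |
| 2 | 0 | count is 0, no percentage printed | count is 0, no percentage printed |

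**Reading the table.**

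- S = T: the percentages are right, even if the two groups are different people, because only the counts enter the formula.
- 0 < S < T: every reason is understated by the factor S/T. With T = 4 and S = 2 for two different reasons, each prints as 1/4 = 25% instead of 1/2 = 50%.
- S > T > 0: the reasons total more than 100%, and a single reason shared by all S patients does so on its own.
- T = 0 and S > 0: a positive count has no computable percentage. The rule "If a count is 0, no percentage will be shown" in SAP Section 4 does not cover this, since the zero is in the denominator. The same section has a convention to show results that cannot be determined as NA, NE or similar.

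**Which direction is likelier.** Protocol 9.3 keeps patients who stop drug in follow-up, and it lists a serious adverse event associated with SARS-CoV-2 infection as a ground for stopping randomized treatment. Both make T larger than S. A patient who leaves the study while still on drug also ends treatment, probably with the same recorded reason, which adds one to each count. S exceeds T only when enough patients leave the study for COVID-19 without a treatment stop for COVID-19, for example after completing treatment but before the safety follow-up visit, or after stopping drug for another reason.

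**The case against.** The strongest reply is that this is a slip with little practical effect. The percentages are wrong only if S and T differ, and the documents give neither count. Only the reason sub-lines of one row are exposed: the parent row is based on randomized patients, and the other reason rows are correct. Counts are printed beside percentages (SAP Section 4), and the listings give each patient's reasons for leaving treatment or study, so a careful reader could detect and correct a mismatch. All of this stands, and it limits the point to a minor correction. It does not make the denominator right.

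A reader might infer more from the mismatch than the documents support:

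- **That the percentages are wrong in every part regardless of the data.** They are right when the two counts are equal, and no percentage is shown when nobody leaves the study for COVID-19.
- **That totals above 100% are to be expected.** The provision in Protocol 9.3 leads to understatement. Exceeding 100% needs S > T, by the less usual routes described above.
- **That the tables would fail on a zero denominator.** The SAP's NA/NE convention covers the display, although a positive count would then have no percentage.
- **That the row's lack of a named Part/Period is a separate defect.** Several other entries in these lists omit it too, including the COVID-19 treatment denominator, and each list is scoped by its opening line. Naming it is only a clarification.

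**Conclusion.** The point holds in limited form. In all three lists of SAP 6.1, the denominator for COVID-19 reasons for leaving the study is the wrong group, and nothing elsewhere in the SAP or protocol corrects it. Followed exactly, the rule gives wrong sub-line percentages whenever at least one patient leaves the study for COVID-19 and the two counts differ.

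The size depends on counts that are not in the documents and are likely to be small. The error factor is S/T, more probably below 1 than above it. Understatement is also harder to notice, because a figure such as 25% looks plausible where 300% does not.

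The totals assume one reason per patient. The mismatch itself does not depend on that assumption. No efficacy or safety result changes.

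**What to change.** In the Part A Period 1, Part A Period 2 and Part B lists of SAP 6.1, change the denominator under the COVID-19 study-discontinuation row to: *the number of patients who discontinued the study due to COVID-19 in that Part/Period*. The reasons then total 100% whenever anyone is in the row (one reason per patient), and no positive count can have a zero denominator. For clarity, the Part/Period could be named in the COVID-19 treatment denominators in the same edit.

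The cost is one phrase in three places, plus a check that the mock tables and programs for Tables 14.1.1.1 to 14.1.1.3 agree. The mock tables are not in the documents reviewed, so whether they repeat the error is unknown. Because SAP text changes, the SAP's allowance for minor mock-table changes without re-approval (Section 4) would not apply. If the SAP is already final, a short note in the study report stating the denominator used would serve.
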